### **1.8 Summary of clinical studies**

The first-in-human phase 1a/1b study with TP-0903, TP-0903-101 (Clinicaltrials.gov identifier: NCT02729298) is ongoing in patients with refractory solid tumors. The Phase 1a study is designed to identify the maximum tolerated dose (MTD) and to identify the safety profile and recommended phase 2 dose of TP-0903. Once the MTD has been established, 5 additional cohorts of up to 20 patients each with specific tumor type will be enrolled at the MTD in the phase 1b study. TP-0903 is administered once daily for 21 days followed by a 7-day drug-free period for one cycle. Patients are allowed to continue on TP-0903 if it shows benefit and is reasonably well tolerated. As of August 2018, adverse events observed in patients treated at the first 7 dose levels are shown in Table 2. Patients are consistently presenting with nausea/vomiting, diarrhea, and anorexia and no DLTs have been observed. Thus far, TP-0903 has been well tolerated with no patients coming off study due to drug-related toxicity. As of March 2019, a flat dose of 50 mg daily on days 1-21 of a 28 day cycle is the dose that will be used for future phase 1b expansion cohorts.

**Table 2.** Treatment-emergent adverse events by body system and preferred term by dosing cohort (safety population and overall).

MedDRA System Organ Class a MedDRA Preferred Term	BSA-based Dose (mg/m  )										Flat Dose (mg)
	Cohort 1 1.5 (n=3)	Cohort 2 3.0 (n=3)	Cohort 3 6.0 (n=3)	Cohort 4 9.0 (n=3)	Cohort 5 12 (n=3)	Cohort 6 16 (n=5 b )	Cohort 7 21 (n=3)	Cohort 8 28 (n=6)	Cohort 9 37 (n=6 c )	Cohort 10 50 (n=3)	
Metabolism and nutrition disorders (cont)											
Hypokalaemia	0	0	0	1 (33.3%)	1 (33.3%)	1 (20.0%)	0	0	1 (16.7%)	0	
Hyperglycaemia	0	1 (33.3%)	0	0	0	0	0	2 (33.3%)	0	0	
Hypocalcaemia	0	1 (33.3%)	1 (33.3%)	0	0	0	0	0	1 (16.7%)	0	
Hyponatraemia	0	0	0	1 (33.3%)	0	1 (20.0%)	0	0	0	0	
Musculoskeletal and connective tissue disorders											
Back pain	0	3 (100%)	0	0	0	2 (40.0%)	0	1 (16.7%)	2 (33.3%)	0	
Musculoskeletal pain	0	0	1 (33.3%)	0	1 (33.3%)	0	1 (33.3%)	1 (16.7%)	0	0	
Musculoskeletal chest pain	0	0	0	0	0	1 (20.0%)	1 (33.3%)	1 (16.7%)	0	0	
Myalgia	1 (33.3%)	1 (33.3%)	0	0	0	0	0	1 (16.7%)	0	0	
Nervous system disorders											
Dizziness	1 (33.3%)	0	0	0	0	3 (60.0%)	0	2 (33.3%)	0	0	
Dysgeusia	0	0	1 (33.3%)	0	2 (66.7%)	1 (20.0%)	0	1 (16.7%)	0	0	
Headache	0	0	0	1 (33.3%)	1 (33.3%)	0	0	1 (16.7%)	1 (16.7%)	0	
Psychiatric disorders											
Insomnia	1 (33.3%)	0	0	0	1 (33.3%)	1 (20.0%)	0	0	1 (16.7%)	0	
Respiratory, thoracic and mediastinal disorders											
Dyspnoea	0	1 (33.3%)	0	0	0	1 (20.0%)	0	2 (33.3%)	0	0	
Cough	0	0	1 (33.3%)	0	0	0	0	2 (33.3%)	0	0	
Oropharyngeal pain	0	0	0	0	0	1 (20.0%)	0	1 (16.7%)	0	1 (33.3%)	
Skin and subcutaneous tissue disorders											
Dry skin	1 (33.3%)	0	0	0	1 (33.3%)	0	0	0	0	1 (33.3%)	
MedDRA System Organ Class a MedDRA Preferred Term	BSA-based Dose (mg/m  )										Flat Dose (mg)
	Cohort 1 1.5 (n=3)	Cohort 2 3.0 (n=3)	Cohort 3 6.0 (n=3)	Cohort 4 9.0 (n=3)	Cohort 5 12 (n=3)	Cohort 6 16 (n=5)	Cohort 7 21 (n=3)	Cohort 8 28 (n=6)	Cohort 9 37 (n=6)	Cohort 10 50 (n=3)	
Blood and lymphatic system disorders											
Anaemia	0	0	1 (33.3%)	0	0	2 (40.0%)	1 (33.3%)	1 (16.7%)	2 (33.3%)	1 (33.3%)	
Thrombocytopenia	0	0	0	1 (33.3%)	1 (33.3%)	0	0	2 (33.3%)	2 (33.3%)	0	
Leukopenia	0	0	1 (33.3%)	0	0	0	0	1 (16.7%)	0	0	
Cardiac disorders											
Tachycardia	1 (33.3%)	0	0	0	0	1 (20.0%)	0	1 (16.7%)	0	0	
Gastrointestinal disorders											
Vomiting	2 (66.7%)	1 (33.3%)	1 (33.3%)	1 (33.3%)	2 (66.7%)	3 (60.0%)	2 (66.7%)	5 (83.3%)	6 (100%)	3 (100%)	
Nausea	1 (33.3%)	1 (33.3%)	1 (33.3%)	0	2 (66.7%)	4 (80.0%)	3 (100%)	5 (83.3%)	4 (66.7%)	3 (100%)	
Diarrhoea	0	0	0	1 (33.3%)	0	3 (60.0%)	1 (33.3%)	5 (83.3%)	3 (50.0%)	2 (66.7%)	
Constipation	1 (33.3%)	1 (33.3%)	0	0	0	2 (40.0%)	1 (33.3%)	0	3 (50.0%)	2 (66.7%)	
Abdominal pain	0	0	0	0	0	2 (40.0%)	0	4 (66.7%)	1 (16.7%)	0	
Abdominal pain upper	0	0	0	0	1 (33.3%)	0	1 (33.3%)	0	1 (16.7%)	0	
General disorders and administration site conditions											
Fatigue	0	1 (33.3%)	0	1 (33.3%)	2 (66.7%)	1 (20.0%)	1 (33.3%)	3 (50.0%)	3 (50.0%)	0	
Oedema peripheral	0	1 (33.3%)	0	1 (33.3%)	0	2 (40.0%)	2 (66.7%)	0	0	0	
Asthenia	0	0	0	0	0	1 (20.0%)	1 (33.3%)	1 (16.7%)	1 (16.7%)	0	
Disease progression	1 (33.3%)	1 (33.3%)	0	0	0	1 (20.0%)	0	1 (16.7%)	0	0	
Pyrexia	1 (33.3%)	0	0	0	0	0	1 (33.3%)	1 (16.7%)	1 (16.7%)	0	
Infections and infestations											
Urinary tract infection	0	0	1 (33.3%)	1 (33.3%)	0	1 (20.0%)	1 (33.3%)	1 (16.7%)	1 (16.7%)	0	
Investigations											
Weight decreased	2 (66.7%)	0	0	0	1 (33.3%)	2 (40.0%)	0	0	0	0	
Metabolism and nutrition disorders											
Decreased appetite	2 (66.7%)	1 (33.3%)	1 (33.3%)	0	2 (66.7%)	1 (20.0%)	0	2 (33.3%)	1 (16.7%)	0	
Dehydration	0	0	0	0	2 (66.7%)	2 (40.0%)	1 (33.3%)	1 (16.7%)	1 (16.7%)	0	
Hypoalbuminaemia	0	1 (33.3%)	1 (33.3%)	0	0	1 (20.0%)	2 (66.7%)	1 (16.7%)	1 (16.7%)	0	
Hypomagnesaemia	1 (33.3%)	0	1 (33.3%)	2 (66.7%)	0	0	0	1 (16.7%)	1 (16.7%)	0	

## 1.9. Rationale and Hypothesis

In biochemical and cellular assays, we showed that TP-0903 can overcome drug resistance from acquired

*FLT3* TKD mutations, including the gatekeeper F691L mutation, which current clinical candidate *FLT3* inhibitors are susceptible to. In *ex vivo* testing of primary *FLT3*-ITD+ leukemia samples, including those harboring a TKI-resistance conferring *FLT3*-ITD/*IDH2* mutation, TP-0903 was more potent than other *FLT3* TKIs. *In vivo*, TP-0903 delayed the outgrowth of leukemia and prolonged survival in xenograft models of *FLT3*-ITD+ AML. Collectively, our preclinical data demonstrate that TP-0903 has activity in *de novo* and TKI-resistant *FLT3*-ITD+ AML with the potential to be a best-in-class *FLT3* TKI, and provide strong scientific premise to conduct a phase 1b/2 trial of TP-0903 in patients with *FLT3*-ITD+ AML. Previous studies have shown that responses with single-agent *FLT3* TKI therapy are generally short-lived, which has led to the evaluation of several TKIs in combination with chemotherapy in phase II/III trials [15, 18, 21, 49, 50]. Therefore, we propose to evaluate TP-0903 as monotherapy for *FLT3*-ITD+ AML patients with relapsed or refractory disease. We hypothesize that TP-0903 will have immediate clinical impact in *FLT3*-ITD+ AML.

## 2. Patient Selection

### 2.1. Eligibility Criteria

**2.1.1.** Patients age  $\geq 18$  with relapsed/refractory AML and the presence of *FLT3*-ITD mutation.

**2.1.2.** Patients with secondary AML or therapy related disease (t-AML) are eligible.

**2.1.3.** If the patient has co-morbid medical illness, life expectancy attributed to this must be greater than 6 months.

**2.1.4.** ECOG performance status  $\leq 2$

**2.1.5.** Patients must have adequate organ function as defined below:

- Total bilirubin  $< 2.0 \text{ mg/dL}$  unless due to Gilbert's disease
- AST (SGOT)/ALT (SGPT)  $< 2.5 \times$  institutional upper limit of normal
- Cr clearance  $> 50 \text{ mL/min}$  by Cockcroft-Gault calculation
- NYHA CHF Class II or better
- Cardiac ejection fraction  $\geq 40\%$

**2.1.6.** Female patients of child-bearing potential must agree to use dual methods of contraception and have a negative serum pregnancy test at screening, and male patients must use an effective barrier method of contraception if sexually active with a female of child-bearing potential. Acceptable methods of contraception are condoms with contraceptive foam, oral, implantable or injectable contraceptives, contraceptive patch, intrauterine device, diaphragm with spermicidal gel, or a sexual partner who is surgically sterilized or post-menopausal. For both male and female patients, effective methods of contraception must be used throughout the study and for three months following the last dose.

**2.1.7.** Ability to understand and willingness to sign the written informed consent document.

**2.1.8.** HIV infection without history of AIDS and sufficiently high CD4 cells ( $> 400/\text{mm}^3$ ) and low

HIV viral loads (<30,000 copies/ml plasma) not requiring anti-HIV therapy are eligible.

## **2.2. Exclusion Criteria**

**2.2.1.** Patients with acute promyelocytic leukemia.

**2.2.2.** Patients who have had chemotherapy or radiotherapy within 2 weeks (6 weeks for nitrosoureas or mitomycin C) prior to entering the study. Treatment with hydroxyurea is permitted during cycle 1 to maintain WBC< 40,000/uL.

**2.2.3.** Patients receiving any other investigational agents or patients that have received other investigational agents within 14 days of enrollment.

**2.2.4.** Patients with *active* CNS malignancy.

**2.2.5.** Major surgery within 2 weeks before Day 1.

**2.2.6.** Uncontrolled active infection. Patients with infection requiring parenteral antibiotics are eligible if the infection is controlled.

**2.2.7.** Patients with significantly diseased or obstructed gastrointestinal tract.

**2.2.8.** Uncontrolled intercurrent illness including, but not limited to, symptomatic congestive heart failure (New York Heart Association (NYHA) Class III or IV), unstable angina pectoris, myocardial infarction within 6 months prior to enrollment, severe uncontrolled ventricular arrhythmias, or electrocardiographic evidence of acute ischemia or active conduction system abnormalities. Prior to study entry, any ECG abnormality at screening has to be documented by the investigator as not medically relevant.

**2.2.9.** Patients with serious medical or psychiatric illness likely to interfere with participation in this clinical study.

**2.2.10.** Pregnant women or women who are breastfeeding are excluded from this study. Confirmation that the subject is not pregnant must be established by a negative serum  $\beta$ -human chorionic gonadotropin ( $\beta$ -hCG) pregnancy test result obtained during screening. Pregnancy testing is not required for post-menopausal or surgically sterilized women.

**2.2.11.** Patients with advanced malignant solid tumors.

**2.2.12.** Patients who are not able to swallow capsules or tablets.

## **2.3. Inclusion of Women and Minorities**

Both men and women and members of all races and ethnic groups are eligible for this trial.

### 3. Treatment Plan

[figure not shown]
#### **TP-0903 MONOTHERAPY FOR AML PATIENTS WITH FLT3 MUTATIONS AND RELAPSED/REFRACTORY DISEASE**

AML patients with FLT3 mutations and relapsed/refractory disease are eligible to receive TP-0903, at a starting dose of 50 mg daily as a single agent for days 1-21 of a 28-day cycle. If the 50 mg dose does not meet the tolerability criteria, a lower dose level of 37 mg daily as a single agent for days 1-21 of a 28-day cycle will be considered.

Dose Level	TP-0903 (D1-21) (mg/day PO)
-1	25
0	37
1	50

Patients may continue treatment indefinitely for as long as clinical benefit is achieved per the investigator's judgment. Bone marrow examinations for disease response assessment will be mandated after the first cycle and at the end of treatment. Subsequent bone marrow examinations may be completed at the discretion of the treating physician.

#### Schema:

**Abbreviations:** AlloHSCT, allogeneic hematopoietic stem cell transplant; CR, complete remission; CRh, complete remission with incomplete count recovery; MLFS, morphologic leukemia free state

### **3.1. Duration of Follow-up**

Patients will be followed monthly for treatment failure until the time of transplant or maintenance therapy, at which time they will go to clinical follow-up, followed every 3 months for up to 2 years from registration and then every 6 months for up to 5 years from registration until relapse or death. Patients who end treatment for reasons other than relapse or a subsequent AML treatment (excluding transplant) will follow the same clinical follow-up schedule. Patients who relapse or receive a subsequent AML therapy (excluding transplant) will go to survival follow-up, followed every 6 months for 5 years from registration until death or the completion of the study. A survival follow-up visit can be conducted by phone or electronic contact with the patient or authorized representative. Please see the study calendar in Section 9 for details.

### **3.2. Recommended supportive care treatment and special considerations**

#### **3.2.1. Nausea**

Patients experiencing Grade ≤ 2 nausea or vomiting on any dose level should be instructed to take prochlorperazine by mouth 10 mg every 6 hours as needed. Patients experiencing Grade 3 nausea on any dose level should be instructed to take 10 mg of prochlorperazine by mouth 30 minutes before their scheduled dose of TP-0903. Additional doses of prochlorperazine may be given on an as needed basis (10 mg every 6 hours). If this is ineffective, patients may receive ondansetron 4 mg as an alternative, but will need an EKG checked prior to starting given the risk for increasing QTc interval.

#### **3.2.2 Diarrhea**

Patients experiencing Grade ≤ 3 diarrhea should be instructed to take loperamide following each loose bowel movement (4 mg initial dose, followed by 2 mg after every loose bowel movement; maximum dose is 16 mg daily).

## **4. Definition of Dose Limiting Toxicity (DLT)/Dosing Delays and Treatment Modifications**

### **4.1. Definition of Dose Limiting Toxicity (DLT)**

Drug-related toxicity in this population may be difficult to ascertain, given the aggressive nature of the underlying hematologic disease. Investigators will attempt to assign attribution of toxicities to each drug if possible. Toxicity attributed to any of the agents will be considered dose limiting. DLT will be assigned only to adverse events occurring with cycle 1 of therapy.

Patients who experience dose limiting toxicity may continue on trial provided that the toxicity has resolved to at least Grade 2. The National Cancer Institute Common Terminology Criteria for Adverse Events (CTCAE) version 5.0 (<http://ctep.cancer.gov>) will be used to characterize toxicities. However, any adverse reaction that leads to dose reduction or withdrawal will be considered a DLT.

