#### **Hematologic toxicity:**

Any ≥ Grade 4 neutropenia lasting more than 14 days past the end of the cycle (by day 42) in the absence of active AML should be considered DLT. For patients with > 5% blasts, myelodysplastic changes, or evidence of disease by flow cytometry/cytogenetics, failure to recover normal neutrophil count will not be considered DLT as this could be the result of persistent disease. Any patients who stop treatment prior to completing evaluation for the DLT observation period due to disease progression or refusal for further participation for reasons other than toxicity will be replaced for the purposes of dose- finding and safety evaluations.

Other events may occur which do not meet the definition of a DLT but are concerning to the investigators and sponsor and may be then considered to be DLTs. Any other toxicities occurring during subsequent cycles after cycle 1 will lead to dose modifications as specified below. The National Cancer Institute Common Terminology Criteria for Adverse Events (CTCAE) version 5.0 (<http://ctep.cancer.gov>) will be used to characterize toxicities.

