#### **4.2. Dosing Delays/Dose Modifications**

##### **4.2.1 Dosing Delays/Dose Modifications for DLTs:**

###### **4.2.1.1 Non-hematologic DLT:**

**Study treatment will be held for any patients experiencing a DLT.**

Patients experiencing Grade  $\geq$  3 non-hematologic toxicity will have study treatment held until the toxicity resolves to NCI CTCAE  $\leq$  grade 1 or to the patient's baseline values. Patients may restart TP-0903 at the next lower dose level when the adverse event recovers to CTCAE  $\leq$  grade 1. If study treatment is restarted and another non-hematologic DLT (Grade  $\geq$  3) is encountered at the lower dose, the patient must be removed from the study. If the non-hematologic toxicity does not recur on re-challenge, the dose level may be re-escalated at the initiation of next cycle at the discretion of the investigator. Study treatment will be discontinued permanently for any grade 4 non-hematologic DLT.

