#### **4.2.1.2 Hematologic DLT:**

After the 42 day period and confirmed hematologic DLT: If peripheral blasts are absent AND bone marrow blasts are less than 5%, then the patient may restart study treatment on cycle 2 at the next lower dose level.

After achieving CR, the dose level may be re-escalated at the initiation of next cycle at the discretion of the investigator.

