### **4.2.2 Dose Delays/Dose Modifications for Non-DLTs**

#### **4.2.2.1 Induction**

Patients experiencing non-DLT toxicities during induction related believed to be due to TP-0903 therapy that present a challenge to medical management (i.e. grade 2 chronic nausea, myalgia, or fatigue) should have their dose held until it falls to a level of grade 1 or < and then re-start at a -1 dose reduction in therapy. If this recurs at the lower dose, the patient will discontinue TP-0903 and be followed on the treatment regimen.

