##### **Hematologic toxicities**

TP0903 dose reductions in subsequent cycles after CR/CRI is achieved (i.e., Subsequent cycles after being in CR/CRI for at least 1 cycle) will depend on the counts prior to starting the preceding cycle.

- a) If prior to the previous cycle (for e.g., patient is starting C5, check the counts prior to starting C4) if the counts were: WBC  $\geq$  3.0  $\times 10^9$ /L, ANC  $\geq$  1.5  $\times 10^9$ /L, and platelets  $\geq$  75.0  $\times 10^9$ /L (all three must apply), adjust the dose as follows, based on nadir counts of the prior cycle (per the e.g. above the prior cycle will be C4):

Nadir Counts		% Dose TP- 0903 in the Next Course
ANC ( $\times 10^9/L$ )*	Platelets ( $\times 10^9/L$ )*	
<0.5	<25.0	50%

\* Dose reductions applies when either ANC OR Platelets are at these values

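### Sections 4.1, 4.2.1.1 and 4.2.1.2 give conditions for continuing after a DLT that do not agree, and the hematologic restart rule states no neutrophil condition of its own

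*Combined protocol and SAP*

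**What the plan says.** Four places in Section 4 bear on what happens after a toxicity.

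- **Section 4.1 (definition of DLT).** "Patients who experience dose limiting toxicity may continue on trial provided that the toxicity has resolved to at least Grade 2". The sentence covers all DLTs and makes no exception by type or by initial grade.
- **Section 4.2.1.1 (non-hematologic DLT).** Treatment is held for grade 3 or higher toxicity until it reaches at most "grade 1 or to the patient's baseline values". The next sentence reads "Patients may restart TP-0903 at the next lower dose level when the adverse event recovers to CTCAE" grade 1 or lower, and does not repeat the baseline alternative. The section ends: "Study treatment will be discontinued permanently for any grade 4 non-hematologic DLT".
- **Section 4.2.1.2 (hematologic DLT).** This applies once day 42 has passed and the DLT is confirmed. "If peripheral blasts are absent AND bone marrow blasts are less than 5%, then the patient may restart study treatment on cycle 2", one dose level lower. No neutrophil count or neutropenia grade appears in the restart condition. The DLT itself is defined in Section 4.1 as grade 4 or higher "neutropenia lasting more than 14 days past the end of the cycle (by day 42) in the absence of active AML should be considered DLT".
- **Section 4.2.2.1 (non-DLT toxicity in induction).** Patients "should have their dose held until it falls to a level of grade 1" or lower and then resume at a reduced dose.

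The only other count-based dosing rule is in Section 4.2.2.2. It sets dose reductions in cycles after CR/CRi, which "will depend on the counts prior to starting the preceding cycle".

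**The concern.** These sections sit within a few paragraphs of each other and address closely related decisions, but they name different conditions: grade 2, grade 1, grade 1 or baseline, and blast clearance without a count. Nothing says which prevails. Two investigators who both follow the text could handle the same patient differently, one resuming drug and the other not.

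The first stake is participant safety, because the text governs re-exposure after a dose-limiting event. The second is interpretation. Section 10 uses the number of TP-0903 cycles received and the reasons for discontinuation to assess tolerability, and both depend on how the restart condition is read.

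**Working it through.** The plan states no figure on this point, so the check sets the sections side by side. I read resolution to at least grade 2 in Section 4.1 as grade 2 or lower.

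**Non-hematologic DLT: Section 4.1 against Section 4.2.1.1**

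| Situation | 4.1 condition | 4.2.1.1 restart condition | Agree? |
|---|---|---|---|
| Grade 3, resolves to grade 1 or lower | met | met | yes |
| Grade 3, stays at grade 3, baseline lower | not met | not met | yes |
| Grade 3, settles at grade 2, baseline grade 1 or lower | met | not met; hold continues | no |
| Grade 3, settles at grade 2, baseline grade 2 | met | hold ends at baseline, but restart condition not met | no, and 4.2.1.1 is inconsistent within itself |
| Grade 4, later resolves | met | treatment permanently stopped | no |

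**Hematologic DLT: Section 4.1 against Section 4.2.1.2** (peripheral blasts absent, marrow blasts below 5%)

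| Neutropenia when restart is considered | 4.1 condition, if it applies | 4.2.1.2 condition | Agree? |
|---|---|---|---|
| Recovered to grade 2 or lower | met | met | yes |
| Still grade 3 or 4 | not met | met | no |

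The blast criteria in Section 4.2.1.2 add little. Section 4.1 counts prolonged neutropenia as a DLT only without active AML, and excludes patients with more than 5% blasts or other evidence of disease. A patient with a confirmed hematologic DLT has therefore largely met the restart criteria already. Section 4.2.2.2 does not fill the gap: it sets dose reductions after at least one cycle in CR/CRi, not a recovery condition after a cycle 1 DLT.

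**Related check.** Section 4.2.2.1 requires grade 1 or lower after a lesser, non-DLT toxicity, which is stricter than the grade 2 that Section 4.1 states for a DLT. Section 4.1 also classes any reaction that leads to dose reduction as a DLT, whereas Section 4.2.2.1 prescribes dose reduction for events it calls non-DLT. The definitional overlap is a separate question, but the wording should be checked in the same edit.

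**Effect on the design.** The tolerability rule (at most 1 of 6) and the phase 2 monitoring table count patients with a DLT in cycle 1. A patient is counted when the DLT occurs, whatever happens at restart. The Simon rule (stop at 4 or fewer of 13; 13 or more of 31 at the end) counts CR/CRh among all eligible patients who start therapy. The restart condition enters none of these rules.

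**The case against.** The strongest reply is that the sections govern different decisions. Section 4.1 speaks of continuing on trial, Section 4.2.1.1 of restarting drug. Grade 2 would then be a necessary condition for remaining in the study, and grade 1 or lower the further condition for dosing. A patient at grade 1 satisfies both, and one permanently off drug for a grade 4 event can stay in follow-up under Section 3.1. This reading is coherent and could reconcile the grade 2 and grade 1 statements and the grade 4 case. But the protocol never draws the distinction, and Section 4 as a whole is headed as covering dosing delays and treatment modifications. The reading also leaves two gaps: the baseline alternative that appears in the hold but not in the restart sentence, and the absence of a neutrophil condition in Section 4.2.1.2.

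A second reply is that Section 4.1, being general, already adds a grade 2 condition to the hematologic rule. That is possible, but it is not stated, and it uses Section 4.1 as a dosing rule, which the first reply denies. It does mean a reader should not infer that the protocol as a whole requires no neutrophil recovery; only Section 4.2.1.2 read alone is silent. That section also lowers the dose at restart and ties re-escalation to achieving CR, which Section 7.1 defines with a neutrophil count of at least 1.0 × 10⁹/L. Those limits govern the dose level, not whether drug may be resumed.

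Third, the baseline mismatch may be a drafting slip, since a hold that ends at baseline naturally implies that dosing can resume. That is fair, and the edit is correspondingly small.

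**Conclusion.** The inconsistency is real and should be reconciled because it bears on re-exposure after a dose-limiting event. It is a contradiction between sections, not a fault in the statistical design.

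Its reach is limited to the four groups below, and the documents give no basis for estimating how many patients they contain:

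- a non-hematologic DLT that settles at grade 2;
- a baseline above grade 1;
- a grade 4 non-hematologic DLT;
- a hematologic DLT without count recovery.

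For the first and third groups the conflict assumes that continuing on trial includes dosing. For the fourth it depends on whether Section 4.1 governs hematologic DLTs.

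Stronger conclusions that a reader might draw are not supported:

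- **Every patient with a DLT is affected.** A grade 3 event that resolves to grade 1 or lower gets the same answer from both sections.
- **About a third of patients are affected.** The phase 2 table suspends accrual at 12 of 31, so 11 of 31 (11/31 = 35%) is the largest DLT count short of suspension at full accrual. It is a ceiling on DLTs, not an expected rate, and not all of those patients would meet conflicting rules.
- **Every hematologic DLT is still grade 4 at restart.** Grade 4 is established when the DLT is confirmed. No restart date is fixed, so counts may recover first; Section 4.2.1.2 merely does not require it.
- **Sites would diverge.** Accrual is projected from one institution, although the drug accountability text mentions several centers. Divergence between investigators is the safer statement.

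**What to change.** Reconcile Sections 4.1, 4.2.1.1 and 4.2.1.2 into one rule for what follows a DLT, cross-referenced from each, and check Section 4.2.2.1 against it. The rule should state:

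1. whether continuing on trial in Section 4.1 means re-dosing or only remaining in the study;
2. whether return to baseline grade permits restart as well as ending the hold;
3. how grade 4 events are handled, in the same terms in both places;
4. whether a neutrophil condition applies after a hematologic DLT, and if so which.

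The clinical team must choose the thresholds; this review takes no position on them. The cost is a protocol amendment to a few adjoining paragraphs. Depending on the thresholds chosen, some restarts may come later or not take place. Sample size, monitoring boundaries and the analysis plan need no change.

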### TP-0903 monotherapy, (Cycle 1 only)

	Screening*	Induction														End-of-Treatment 	Follow-up 				
		D1	D2	D3	D4	D5	D6	D7	D8	D9	D10	D11	D12	D13	D14	D15	D16	D18	D21	D28	
Medical History	x																			x	
Complete Physical exam and ECOG PS	x																			x	x
Weight and BSA	x	x				x												x	x	x	
Symptom directed physical evaluation		x				x						x					x		x	x	
Vitals signs 	x	x				x						x						x	x	x	x
12-Lead Electrocardiogram (ECG) 		x	x																	x	
Serum pregnancy test 	x																			x **if fertile female only	
CBC 	x	x				x						x						x	x	x	x
Complete Serum chemistry 	x	x				x						x						x	x	x	x
Coagulation tests (PT and PTT)	x	x				x						x								x	
TP-0903 dosing in Clinic/Home/Inpatient 		x	x	x	x	x	x	x	x	x	x	x	x	x	x	x	x	x	x		
Bone Marrow (BM) aspiration and biopsy 	x					x												x			

Adverse event and Toxicity evaluation 	x				x					x				x	x	x	
Correlative Studies 	x	x			x					x				x	x		

\* \*Treatment may begin on the same day as screening.

 Vital signs including blood pressure [BP], heart rate [HR], respiratory rate [RR], temperature [T] pulse oximetry (POX) and weight will be assessed prior to administration of TP-0903.

 ECGs: to be performed in the supine position at screening and day 1 of the first cycle.

 Applies to women of childbearing potential (WOCP) only. WOCP must have a negative pregnancy test within 2 weeks prior to the initiation of therapy.

 Complete Blood count with differential will be performed about twice weekly during induction and then as clinically indicated.

 Complete serum chemistries includes: Sodium, Potassium, Chloride, Bicarbonate, Creatinine, BUN, Glucose, Phosphorus, Albumin, Total bilirubin, SGOT (AST), SGPT (ALT), Alkaline phosphatase and LDH Women of childbearing potential must have a negative pregnancy test within 2 weeks prior to the initiation of therapy.

 TP-0903 will be administered per section 3.

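### A cycle 1 dose reduction ordered by Section 4.2.2.1 for a toxicity it calls non-DLT is a DLT under Section 4.1, so the 1-of-6 dose gate can be counted two ways

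*Combined protocol and SAP*

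**What the plan says.** Section 4.1 sets the window: "DLT will be assigned only to adverse events occurring with cycle 1 of therapy". Its next paragraph, in a sentence opening with However, adds a criterion with no grade limit: "any adverse reaction that leads to dose reduction or withdrawal will be considered a DLT".

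Section 4.2.2 covers dose changes for events that are not DLTs. Its first part, 4.2.2.1, is addressed to "Patients experiencing non-DLT toxicities during induction related believed to be due to TP-0903 therapy" that are hard to manage medically, with chronic grade 2 nausea, myalgia and fatigue as examples. The drug is held until grade 1 or lower, "and then re-start at a -1 dose reduction in therapy". Then: "If this recurs at the lower dose, the patient will discontinue TP-0903".

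Induction is not formally defined. In Section 9, the calendar for cycle 1 alone carries the column heading Induction, and its blood count footnote says that counts "will be performed about twice weekly during induction and then as clinically indicated". Cycles 2-4 and maintenance have a separate calendar.

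The non-hematologic list in 4.1 makes every toxicity of grade 4 or higher a DLT, with no exception. It makes non-Hy's-law liver abnormalities of grade 3 or higher DLTs unless they resolve within 72 hours. It then makes every other grade 3 or higher toxicity not caused by active leukemia a DLT, apart from five listed exceptions. One exception is a grade 3 or 4 electrolyte disturbance corrected within 24 hours and not clinically significant. Liver events are not on the list.

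Section 10 uses the DLT count twice: in the tolerability check, where at most 1 of 6 passes, and in the phase 2 suspension table for 7 to 31 patients.

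**The concern.** Following 4.2.2.1 in cycle 1 produces the very action that 4.1 says turns an event into a DLT, yet 4.2.2.1 says the event is not one. No precedence is stated, so two careful investigators could classify one patient differently.

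The DLT count is the only input to the six-patient check, and that check decides whether phase 2 runs at 50 mg or the trial moves to 37 mg. A check this small turns on one patient.

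The two conflicts inside the non-hematologic list are lesser drafting points. The electrolyte one has a further consequence if the grade 4 line is read literally: 4.2.1.1 permanently stops treatment for any grade 4 non-hematologic DLT, so a patient with a briefly abnormal electrolyte value would lose the drug.

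**Working it through.** **1. Do the rules overlap?**

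| Question | Section 4.1 | Section 4.2.2.1 |
|---|---|---|
| Period | Cycle 1 | Induction; the cycle 1 calendar is headed Induction |
| Event | Any adverse reaction, any grade | Drug-related toxicity hard to manage, e.g. chronic grade 2 nausea |
| Action | Dose reduction or withdrawal | Reduction; discontinuation on recurrence |
| Status | DLT | Non-DLT |

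Cycle 1 lies inside 4.2.2.1 whether induction means cycle 1 alone or extends further. Section 4.1 also says "Any other toxicities occurring during subsequent cycles after cycle 1 will lead to dose modifications as specified below". That sends later-cycle events to Section 4.2 but does not take cycle 1 out of 4.2.2.1. A reduction made after cycle 1 falls outside the DLT window and is not in dispute.

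**2. The plan's own boundaries.** The suspension rule is the smallest count r with Pr(p > 0.25 | r of n) > 0.95 under a Beta(1 + r, 1 + n − r) posterior. All 25 tabled counts reproduce: each exceeds 0.95, and one fewer does not. At n = 9, 4 DLTs give 0.922 (continue) and 5 give 0.980 (suspend). The rules that use the count are sound; what is unsettled is who is counted.

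**3. One patient at the gate.** Take six patients, one with an undisputed DLT and one with chronic grade 2 nausea whose dose is reduced in cycle 1. Under 4.1 this is 2/6 and 50 mg fails. Under the label in 4.2.2.1 it is 1/6 and 50 mg passes.

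**4. Average effect on the gate.** Let p be the rate of undisputed DLTs and q the rate of patients with only a disputed event. The documents give neither, so both are assumed. The gate passes with probability

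P(X ≤ 1), X ~ Bin(6, π), which equals (1 − π)^5 (1 + 5π),

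with π = p if disputed events are not counted and π = p + q if they are. For example, π = 0.10 gives 0.59049 × 1.5 = 0.886.

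| p | Not counted | Counted, q = 0.02 | Counted, q = 0.05 | Counted, q = 0.10 |
|---|---|---|---|---|
| 0.05 | 0.967 | 0.939 | 0.886 | 0.776 |
| 0.10 | 0.886 | 0.844 | 0.776 | 0.655 |
| 0.15 | 0.776 | 0.729 | 0.655 | 0.534 |
| 0.20 | 0.655 | 0.606 | 0.534 | 0.420 |
| 0.25 | 0.534 | 0.487 | 0.420 | 0.319 |

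The drop is 0.03-0.05 at q = 0.02, 0.08-0.12 at q = 0.05, 0.19-0.24 at q = 0.10, and zero at q = 0.

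**5. Effect on the suspension table.** Start from 0 or 1 DLT in the first six, conditional on passing, and step through patients 7 to 31, stopping when the cumulative count reaches the tabled value. The chance of ever crossing is 0.002, 0.014, 0.051 or 0.137 at a total counted DLT rate of 0.15, 0.20, 0.25 or 0.30. Crossing leads to suspension and data review, not automatic closure. The effect is therefore mainly on the gate.

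**6. The non-hematologic list.** A transient grade 4 electrolyte disturbance is exempt by the list and caught by the grade 4 line. A liver abnormality of grade 3 or higher that resolves within 72 hours is spared by its own line and caught by the general grade 3 line; at grade 4 it is also caught by the grade 4 line.

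**The case against.** The best reply is that 4.1 already supplies the precedence. However, followed by any, is override language: 4.2.2.1 tells clinicians how to manage events that miss the grade criteria, and 4.1 says how to count them once a cycle 1 reduction follows. This is the better reading, and it stands. But the text does not say so, and on that reading no cycle 1 event remains non-DLT once 4.2.2.1 has been carried out, so the label still misleads.

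The overlap is also narrow. The named examples are chronic grade 2 events. Section 3.2.1 directs prochlorperazine for nausea, then ondansetron. The hold and the restart must fit within 21 dosing days, and discontinuation needs a recurrence at the lower dose. This stands too, and it points to a low rate of disputed events, though not to zero.

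A reader might infer that disputed events will be common and that earlier experience left them uncounted, because Table 2 shows nausea in 3 of 3 patients in the 50 cohort and 4 of 6 in the 37 cohort while Section 1.8 reports no DLTs. The documents do not support this. The counts are any grade. The no-DLT statement follows a sentence dated August 2018 about the first 7 dose levels, so it may not cover those two cohorts, which are numbered 9 and 10. Nothing says how many patients had chronic grade 2 nausea or a reduction.

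For the liver and electrolyte lines, reading the specific over the general is natural, since the exemptions would otherwise have little or no effect. That stands, but the text does not state it. The clause in 4.1 letting investigators and sponsor treat other concerning events as DLTs can only add to the count. The monitoring meetings in Section 5.8 discuss DLTs but state no precedence.

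**Conclusion.** The contradiction is real and should be fixed before the first six patients are classified. It is limited to reductions or stops within cycle 1, and 4.1 leans towards counting them. One reclassified patient can reverse the dose decision, but how often that would happen is unknown. The drops in pass probability of 0.03-0.05 and 0.08-0.12 rest on assumed rates of 2% and 5% of patients with only a disputed event and on p between 0.05 and 0.25. The larger drop of 0.19-0.24 needs 10%, for which the documents offer no support.

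A reader might go further and conclude that the DLT definition fails as a whole or that the stopping rules are wrong. Neither follows: other events are classified without this conflict, and every tabled boundary reproduces. Nor does the plan clearly order permanent discontinuation for a transient electrolyte abnormality; that arises only if the grade 4 line is read literally against its own exception.

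**What to change.** 1. In 4.2.2.1, add that a reduction or discontinuation in cycle 1 under this section counts as a DLT per 4.1. Relabel the class as toxicities not meeting the grade-based DLT criteria.
2. In 4.1, make the grade 4 line read: 'Any ≥ Grade 4 non-hematologic toxicity, except as listed below'. Line-associated venous thrombosis is listed without a grade limit, so the sponsor should cap it if grade 4 is not meant to be exempt.
3. Add 'non-Hy's law liver abnormality resolving within 72 hours' to the exceptions. The liver line as written includes grade 4; the sponsor should confirm that this is intended.
4. Use this single definition for the six-patient check, the suspension table and the grade 4 discontinuation rule in 4.2.1.1.

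This is a wording amendment to Sections 4.1 and 4.2. It needs no extra patients or procedures and changes no boundary. The cost is a somewhat stricter gate if 4.2.2.1 reductions would otherwise have gone uncounted, by the amounts given above for 2% and 5%, and no change if there are none. If the sponsor prefers on clinical grounds not to count them, 4.1 must be amended instead.
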